## V. Risks, Benefits, Safety Plans

### V.1. Risks associated with the human study

Potential risks are minimal for the human participant study. Potential risks associated with the procedures and equipment that will be used to collect the exhaled breath CO, topography, and pulmonary data are minimal. Potential risks resulting from collecting blood samples include being unable to provide blood samples because forearm veins are not adequate, feeling light-headed or faint, nausea, dizziness, hematoma or bruising at or near the needle site. We minimize this risk by using certified technicians with extensive experience in collecting blood samples. However, if the participant does not feel comfortable for any reason and wants to end their participation in the study, he/she can do so at any time without penalty. Some of the survey questions may upset individuals; however, we have used these questions and procedures in many previous studies without upsetting participants.

There are no potential risks involved in the collection of waterpipe smoking topography, as the device does not change the resistance to draw or toxicity of the smoke inhaled. The data are acquired continuously to an electronic file, and may be displayed on a laptop screen that is not viewable by either participant. Therefore the possibility of the participant amplifying their puffing rate in order to see the on-screen response is eliminated.

Participants may feel hungry because they will not be permitted to eat until after their post-smoking lung function test is completed. Pulmonary function studies involve forceful respiratory maneuvers and occasionally people develop light-headedness during the procedures or soreness of the chest for a few days. Subjects will be seated and closely monitored by trained/certified personnel during those procedures.

The RWP that participants will smoke at the clinic is specially designed for investigational research only, and as such may have unknown health risks. Both the single- and dual-hose versions of the RWP have been used by participants in several previous studies.

A potential risk is loss of confidentiality. We have rigid procedures in place to protect against loss of confidentiality. Participant identifiers will be kept in a locked file cabinet. This study is not unlike our previous work investigating the efficacy of WP warning labels; we collect the

information and keep it confidential and anonymous through the use of IDs only and not personally identifying information.

De-identified, coded participant data from the general version of the Labeled Magnitude Scale (gLMS) and the Labeled Hedonic Scale (LHS) will be analyzed by [name], Associate Professor, Department of Food Science and Technology, Oregon State University. [name] will receive all scale ratings, matched with participant identification codes, date of participant laboratory visit, period data was collected (e.g., pre-smoking, post-smoking, etc.) and select demographic and tobacco use history data such as sex, age, and how many cigarettes smoked per day. All data sent to [name] will be stripped of participant identifying information.

During an ongoing virus pandemic (such as COVID-19), we will follow strict safety procedures to reduce risk of spread of the disease among the participants and staff. Depending on currently recommended guidelines, these procedures may entail:

- Collecting data on forehead temperature and assessing symptoms of viral infection at each visit
- Wearing personal protective equipment and sanitizing hands
- Routine cleaning of surfaces and equipment
- Implementing physical distancing

## **V.2. Benefits associated with the study**

There are no direct benefits to be gained by participants. However, the anticipated societal benefit resulting from this study is considerable, given the increasing prevalence of WP tobacco smoking. Societal benefits include increased public health resulting from this study providing evidence that directly informs and strengthens FDAs tobacco control efforts. Few studies have been conducted on WP tobacco additives and at the same time, there is mounting evidence that young adults, a vulnerable population from a tobacco control perspective, are largely misinformed of the risks of this form of tobacco use.

## VI. Data Storage

### VI.1. Paper materials

Informed consent forms, receipts, and paper surveys will be stored in locked file cabinets only accessible by study staff. Paper surveys may be shredded after they have been entered in an electronic database.

### VI.2. Electronic data and subject identifying data

REDCap will be used for entry of paper surveys and collection of survey data. Protection against loss of confidentiality and privacy will be maintained by numerically coding all data, disguising identifying information, and keeping data locked in file drawers or in a secure, password-protected database. Only study research assistants and the PIs will have the information that connects participant's name and ID number. All electronic data will be numerically coded and stored in a password protected database, on a password protected computer in a secure research space. Participant information will be accessible only to research staff, who are pledged to confidentiality and complete training in the ethical conduct of research (i.e., both HIPAA and CITI trainings). Identifying information will not be reported in any publication.

## VII. Data Analysis

### VII.1 Analysis Plan

The main research questions from the four Aims in the proposed study have the same structure for data analysis. That is, there are differences attributable to the four tobaccos in the means of the outcome measures of interest. All relevant outcome variables will be first examined with exploratory/descriptive statistical analyses that focus on describing and understanding patterns and distributions for all relevant measures (e.g., tobacco chemical content, mainstream smoke constituents, spirometry measures, topography measures, psychophysical ratings) by the four tobaccos. We will identify any potential outliers, assess distributional assumptions, and apply appropriate transformations to the outcome variables (e.g., log-transformation) if the normality assumption is violated.

For each of the four aims, the following pairwise comparisons will be performed:

$$H0i j: \mu_i = \mu_j \text{ vs. } H1i j: \mu_i \neq \mu_j$$

where  $\mu_i$  = mean target outcome for tobacco type i, and  $\mu_j$  = mean target outcome for tobacco type j. In Aims 1, 2, and 4, the data will be analyzed using one-way ANOVA models for independent outcome data and Tukey's method will be used to control type-I error rate across the six multiple comparisons. A different analysis strategy will be used in Aim 3 due to the clustered study design: participants will complete four different smoking sessions. Thus, in order to account for the hierarchical design, the data in Aim 3 will be analyzed using linear mixed models containing random subject effects. Since linear mixed models allow for incomplete data (e.g.,

due to dropout), data from all completed smoking sessions will be used in the analysis. As in the other aims, Tukey's method will be used to adjust for multiple comparisons of the tobacco treatments in Aim 3. In addition, for Aim 3, we will use linear mixed models to examine the relationships between the perceived sensory intensity ratings and the liking/disliking ratings for a given tobacco preparation.

Integrating results from Aims 1, 2 and 4 with Aim 3 of the study, the absence or presence, or exposure level of certain HPHCs and other chemical compounds across the different tobacco preparations will be mapped with the data on perceived sensory intensity such as sweetness and liking/disliking ratings.

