#### III.C1. Aim 1 Measurement/Instrumentation

Nicotine, humectants, sugars, carbonyls, and semivolatile furans, as detailed in Table III.3, will be determined twice: once at the beginning and once at the end of the human study. Nicotine content of the unburned tobaccos will be determined using gas chromatography with mass spectral detection (GC-MSD). Humectant content will be determined using GC with flame ionization detection (FID), or GC/MS. Sugar content, including sucrose, glucose, and fructose, will be determined using high performance liquid chromatography (HPLC) techniques. Carbonyls will be determined in the tobacco as their 2,4-dinitrophenylhydrazine (DNPH) derivatives using liquid chromatography tandem mass spectrometry. Semivolatile furans will be determined in the tobacco using a liquid chromatography method previously used by our team.

Total aerobic microbial and total yeast and mold counts (TAMC and TYMC) will be determined according to USP 61, after the ITPs are prepared, midway through participant processing, and at the completion of participant processing.

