### III.D1. Aim 1 Detailed Study Procedures

Selection of WP Tobacco. As the starting material for the preparation of the four test tobaccos, we will use a popularly smoked unflavored tobacco (see Unflavored Tobacco in Table II.2) claimed by the manufacturer to “present a plain molasses flavor.” This tobacco has a low glycerol content that is amenable to the proposed product manipulation.

Preparation of WP Tobacco. A popular, commercially available WP tobacco brand (Moassel Saloum) will be prepared four different ways:

- (1) Medium glycerol (60 mg/g), Medium Sugars (350 mg/g)
- (2) High glycerol (120 mg/g), Medium Sugars (350 mg/g)
- (3) Medium glycerol (60 mg/g), High sugars (510 mg/g)
- (4) High glycerol (120 mg/g), High sugars (510 mg/g)

Several packages of the tobacco, purchased from the same source, will be combined, twigs and sticks removed, homogenized, and split into four equal batches. Food grade glycerol, glucose and fructose (>99% purity) will be added to the tobacco to obtain the concentrations shown for the ITPs in Table II.2.

Determination of Nicotine Content. To aid in determining if humectant levels affect the transfer of nicotine from the tobacco into the mainstream smoke, the nicotine content of Batches 1-4 will be individually determined using a method previously qualified by our team. An aliquot (0.25 g) of each tobacco sample will be extracted individually for four hours in a mixture of isopropyl alcohol, methyl tert-butyl ether, and sodium hydroxide using an orbital shaker table at 160 rpm. The extraction solvent mixture will contain a known quantity of quinoline as the internal standard (IS). An aliquot of the extract will be quantitated for total nicotine using gas chromatography with mass spectral detection (GC-MSD).

Determination of Humectant Content. To aid in determining the fraction of humectants transferred to the mainstream smoke and verify the levels of added glycerol, the glycerol and propylene glycol content of each tobacco preparation will be determined using a Health Canada method adopted for use on WP tobacco by Schubert et al.

Determination of Sugars in the Four Tobacco Preparations. The sugar content of the four prepared batches will be quantified. An aliquot (1 g, 3 replicates) of each tobacco preparation will be extracted into HPLC grade water and analyzed using validated methods based on standard liquid chromatography (LC) techniques.

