Determination of Carbonyl Content. To determine the fraction of carbonyls in the tobacco vs. those generated as a result of additives, carbonyls will be determined in the tobacco as their 2,4-dinitrophenylhydrazine (DNPH) derivatives using liquid chromatography tandem mass spectrometry.

Determination of Semivolatile Furan Content. To determine the fraction of semivolatile furans in the tobacco vs. those generated as a result of additives, semivolatile furans will be determined in the tobacco using a liquid chromatography method previously used by our team.

Determination of Aerobic Bacteria, Yeast and Mold. Because sugars and glycerol can function as preservatives in WP tobacco, it is important to document the storage stability of the ITPs. Therefore, the total aerobic microbial and total yeast and mold counts (TAMC and TYMC) will be determined according to USP 61, after the ITPs are prepared, midway through participant processing, and at the completion of participant processing.

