## VII.2. Sample Size Justification.

Since Aims 1, 2, and 4 do not involve human subjects, we expect low variability across replicates. Thus, assuming a somewhat conservative coefficient of variation (CV) of 20% and log-normal outcomes, a total of **4 replicates per tobacco preparation** will provide 80% power to detect a two-fold change in the geometric means of two groups at a conservative two-sided Bonferroni-corrected type-I error rate of 0.0083.

Our sample size for Aim 3 was selected to ensure that we have adequate power to detect moderate effect sizes in our comparisons of topography outcomes. We made the following assumptions for the power analysis:

- Based on the intravariability data analysis for the RWP, correlation coefficients within subjects ( $r$ ) were assumed to be 0.6, 0.7 or 0.8.
- Small, medium, and large effect sizes ( $d$ ) of 0.2, 0.5, and 0.8 standard deviations.
- A two-sided, Bonferroni corrected type-I error rate of 0.0083.

Our power analysis, summarized in Table VII-5, revealed that a sample size of 43 subjects will provide over 80% power to detect a moderate effect size unless the within pair correlation is high (0.2 or 0.3) and the within participant correlation is modest (0.6). However, since this power analysis assumes complete follow-up, we will recruit **60 participants** to account for a possible attrition rate of 20%, and ensure the Latin square ordering is balanced across the four tobacco types.

Table VII.5. Estimated % power to for pairwise comparisons of tobacco preparations based N = 25 pairs (50 subjects).

$r$	$\rho$	Power		
		$d=0.2$	$d=0.5$	$d=0.8$
0.6	0.1	0.108	0.803	0.998
	0.2	0.097	0.759	0.996
	0.3	0.088	0.717	0.994
0.7	0.1	0.153	0.918	> 0.999
	0.2	0.138	0.889	> 0.999
	0.3	0.125	0.857	0.999
0.8	0.1	0.255	0.989	>0.999
	0.2	0.228	0.981	>0.999
	0.3	0.207	0.971	>0.999

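### Aim 1 tobacco content is measured at the start and end of the human study, but the planned one-way ANOVA has no time term, so change over storage is never tested and, if both times are pooled, drift costs power

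*Combined protocol and SAP*

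**What the plan says.** Section III.C1 lists nicotine, humectants, sugars, carbonyls and semivolatile furans in the unburned tobacco and says that they "will be determined twice: once at the beginning and once at the end of the human study".

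Section VII.1 gives the analysis: "In Aims 1, 2, and 4, the data will be analyzed using one-way ANOVA models for independent outcome data". The hypotheses are pairwise differences between tobacco types, and "Tukey's method will be used to control type-I error rate across the six multiple comparisons". There is no time factor, no tobacco-by-time term and no start-versus-end contrast. The descriptive summaries are also broken down by tobacco only.

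Section VII.2 sizes Aims 1, 2 and 4 on replicate variability alone, "assuming a somewhat conservative coefficient of variation (CV) of 20% and log-normal outcomes". It states a total of "4 replicates per tobacco preparation", which "will provide 80% power to detect a two-fold change in the geometric means of two groups" at a two-sided level of 0.0083. For sugars, III.D1 gives a different count: "An aliquot (1 g, 3 replicates) of each tobacco preparation will be extracted into HPLC grade water". Neither section says how replicates divide between the two time points.

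Section III.D1 also says "it is important to document the storage stability of the ITPs". That sentence introduces the microbial, yeast and mold counts, which have their own three-time schedule.

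**The concern.** The second content measurement can show whether the products stayed at their designed levels while participants were smoking them. The plan collects it and then names no analysis that uses it for that purpose. A model with tobacco as its only factor cannot say whether content changed, or whether it changed more in one preparation than in another.

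If start and end samples are put into that one model, samples taken at the same time share whatever shift has occurred. The shift is counted as random error, so the tobacco contrasts lose precision. The contrasts that define the products are 60 v 120 mg/g glycerol and 350 v 510 mg/g sugars. The second is only a 1.46-fold difference (510/350 = 1.457), well below the two-fold change used for sizing, so it has the least power to spare.

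VII.1 also intends to map chemical levels across the preparations to the sensory and liking ratings. If preparations drift differently, one mean per tobacco describes neither the early nor the late product well.

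**Working it through.** **Inputs from the documents.** CV 20% on a log-normal scale, 4 replicates in total per tobacco, four tobaccos, two-sided level 0.05/6 = 0.0083, two-fold target (all VII.1 and VII.2); sugar levels 350 and 510 mg/g (III.D1).

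**Assumptions.** The documents give no drift size, so a loss of 10%, 20% or 30% by study end, common to all four tobaccos, is assumed. The 4 replicates are assumed to split two per time, and both times are assumed to be pooled.

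**The plan's own figure.** The log-scale SD is s = √ln(1 + 0.20²) = 0.198, and the effect is ln 2 = 0.693. A two-sample noncentral t with 4 per group and 6 df gives 80.05% power, which matches the stated 80%. The figure is right on its own inputs; it contains no between-time component.

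**Residual inflation.** With n = 4 values per tobacco, half at each time, and log drift D = ln(1 − loss):

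variance ratio = 1 + n(D/2)² / [(n − 1)s²], with s² = ln 1.04 = 0.0392.

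At a 20% loss, D = −0.223 and (D/2)² = 0.01245. The ratio is 1 + (4 × 0.01245)/(3 × 0.0392) = 1.42, so the SD ratio is √1.42 = 1.19.

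**Power.** The noncentrality is ln(ratio)/(s√(2/4)), with s multiplied by the SD ratio for the one-way model. Error df are 16 − 4 = 12 for one-way, 11 for tobacco + time, and 16 − 8 = 8 with the interaction.

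| Common loss | Variance ratio | SD ratio | 510/350, one-way | Two-fold, one-way |
|---|---|---|---|---|
| 0% | 1.00 | 1.00 | 0.37 | 0.94 |
| 10% | 1.09 | 1.05 | 0.33 | 0.92 |
| 20% | 1.42 | 1.19 | 0.24 | 0.81 |
| 30% | 2.08 | 1.44 | 0.15 | 0.62 |

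A time term removes a common drift, so power does not depend on the loss. With tobacco + time it is 0.36 for the sugar contrast and 0.93 for two-fold. With the full interaction model it is 0.305 and 0.88.

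**Check by simulation with Tukey's method (20,000 data sets per case).** The formula above is approximate: it also widens the spread of the difference, whereas a balanced common drift cancels from it. The simulation avoids this. At 10%, 20% and 30% loss, sugar-contrast power is 0.387, 0.261 and 0.110 one-way, against about 0.42 with time. Two-fold power is 0.945, 0.889 and 0.722, against about 0.95. Levels are a little higher than in the table at small drift because Tukey is less strict than Bonferroni; the pattern is the same.

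**Direction of the error.** With no true differences, the chance of any false Tukey rejection under the one-way model falls from 0.05 to 0.041, 0.016 and 0.003 at the three losses.

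**If there were 4 replicates per time (8 in total).** The variance ratio is 1.08, 1.36 and 1.93. Simulated sugar-contrast power is 0.822, 0.728 and 0.507 one-way, against about 0.85 with time. Two-fold power stays at 0.998 or above.

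**The case against.** Several points on the other side stand.

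- A reader might infer that the plan's error term is inflated as a matter of fact. The documents do not support that. VII.1 does not say that both times enter one ANOVA, and a separate analysis at each time would have no inflation. Inflation also needs real drift, on which the documents are silent. Even so, separate one-way analyses would still not test change.
- A reader might infer invalid tests from the independence assumption. The effect runs the other way: fewer rejections, not false ones.
- A reader might infer that Aim 3 results are biased. VII.1 analyses Aim 3 by tobacco type and does not enter measured content as a participant-level covariate. Each participant smokes all four tobaccos, so common drift largely cancels within person when visits are close together. Only differential drift matters much there, and the calculations above model common drift only.
- The storage-stability sentence concerns microbial counts. It is not a promise to test chemical drift and should not be read as a broken commitment.
- The sentence on one-way ANOVA covers three aims, but the two-time schedule applies to unburned tobacco in Aim 1, not to the smoke yields of Aims 2 and 4.
- A full two-way model with interaction is not free. On the stated total of 4 replicates it uses 4 of 12 error df. At 10% drift it has less power than the one-way model (0.305 v 0.333 for sugars; 0.88 v 0.92 for two-fold). It should not be the model for the main comparisons.

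What remains is that a measurement is scheduled twice and no analysis of the change is specified.

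**Conclusion.** The point holds in a limited form. On any reading, the Aim 1 plan never tests change in tobacco content over storage, although the data for it are collected. If the two times are pooled, drift also costs power: little at 10% loss and substantial by 30%, mainly for the sugar contrast. These sizes rest on an assumed common loss, CV 20%, and two replicates per time.

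Power for the sugar contrast is low on the stated replicate total even without drift (0.37), so a time term prevents further loss and does not rescue that comparison. The human comparisons in Aim 3 are not shown to be wrong. This is a low-cost improvement, not a threat to the trial's conclusions.

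**What to change.** For Aim 1 content only:

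- Add time (start, end) as a factor and make the six tobacco comparisons from the tobacco + time model with Tukey's method.
- Report the start-to-end change for each tobacco with a confidence interval, and the tobacco-by-time term as a separate stability check.
- State how many replicates are run at each time, and reconcile the total of 4 in VII.2 with the 3 given for sugars in III.D1.

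The cost is a few lines of text and 1 error degree of freedom in the main comparison. If there is no drift, power for the sugar contrast goes from 0.370 to 0.357; at 10% drift the time term already gains (0.357 v 0.333). If the replicate total stays at 4, no new samples are needed. The stability check would reveal differential drift but would not itself correct any Aim 3 estimate; if it appears, the mapping of content to ratings should be qualified accordingly.

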### III.B3. Aim 3 Sample

We will recruit a total of 60 healthy adult men and women with the goal of having complete data sets for 50 participants. Participants will meet the eligibility criteria shown in Table III.4. Established waterpipe smokers will be recruited from advertisements

*Table III.4. Participant inclusion and exclusion criteria.*

Inclusion	Justification for Inclusion
Sufficient understanding of consent form and study procedures	Necessary to ensure that participants are adequately informed about the study
Age 21-50 years old	Legally of age to purchase, use, and possess tobacco and provide informed consent
Experienced WP smokers defined as having smoked a WP at least 3 times per month in the last month	To assure that participants are experienced WP smokers, and increase the probability of subjects being able to comfortably smoke
Willing/able to abstain from nicotine product use for at least 12 hours prior to the laboratory visits	Necessary to normalize participants' willingness to smoke WP across visits
Willing to attend four laboratory sessions at the same time of day lasting approximately 3 h each	Necessary to complete all testing sessions and provide adequate power for data analysis
Read and speak English.	To ensure that participants are adequately informed about the study and can follow the
Exclusion	Justification for Exclusion
Evident intoxication on any visit	Intoxication would interfere with informed consent and study procedures
Exhaled breath CO > 10 ppm	Indicates recent combustible tobacco use.
Pregnancy (known or suspected), trying to become pregnant, breastfeeding, unwillingness to use contraception for the duration of the study.	Unethical to enroll pregnant or breastfeeding women for smoking research
Significant smoking-related disease (by history)	Unethical to enroll subjects with tobacco-related diseases

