## IV. Detailed Study Procedures for the Human Study (Aim 3)

Study subjects will participate in a series of 4 laboratory sessions, each visit separated by at least a week, in which they smoke one of 4 tobacco preparations (blinded) using the RWP2, shown in Figure II.1, in a randomly assigned sequence, using the block randomization method. Smoking sessions will be carefully standardized: they will take place in a controlled setting, individual roomsdesignated for smoking research with sufficient ventilation rate at the Center for Tobacco

Research) within one hour of the same time-of-day after overnight nicotine abstinence ( $\geq 8$  hours, exhaled CO  $\leq 10$  ppm^173).

Research staff will light and add the charcoal and record tobacco and charcoal weights. The research-grade waterpipes will be prepared by the laboratory staff, and participants will smoke ad lib to satiation. Participants will be limited to one bowl (15 g) of tobacco and one quick-light charcoal (~10 g).

Prior to the start of the first laboratory visit, a research assistant will explain the study to the participant and answer any questions they may have. The participants will give an exhaled breath sample into the handheld CO monitor to determine if they are eligible to participate in the laboratory smoking session. If the participant's exhaled CO concentration is less than or equal to 10 ppm) they are deemed eligible to participate further, and will be asked to read the informed consent form. Once all participant questions have been answered, the participants will each be asked to sign their consent to participate in the study. Each female participant of child-bearing age will be asked to provide a urine sample for use in conjunction with a "dip-stick" pregnancy test to determine participation eligibility. Female participants with a negative urine pregnancy will be eligible to participate if they provide written agreement (via signing the consent form) to use reliable contraception throughout their participation in the study.

Each participant will then be asked to provide a pre-smoking blood sample by venipuncture. If the phlebotomist is unable to take a sufficient blood sample (10 mL) from the participant, the participant will be deemed ineligible to participate further in the study. Participants will then answer demographic and tobacco use questions.

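### The Aim 3 mixed model names no visit effect although tobacco order is balanced over visits; any shared visit trend then stays in the error and costs power

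*Combined protocol and SAP*

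**What the plan says.** The only description of the Aim 3 model is in section VII.1 (Analysis Plan): "the data in Aim 3 will be analyzed using linear mixed models containing random subject effects". Tukey's method is then applied to the "multiple comparisons of the tobacco treatments in Aim 3", and every completed session contributes data. Tobacco is implied as a fixed effect by the Tukey sentence. Visit, period and sequence appear nowhere as terms. A separate use of mixed models, for "relationships between the perceived sensory intensity ratings and the liking/disliking ratings for a given tobacco preparation", is not at issue here.

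The design is a four-period crossover. Section IV states: "Study subjects will participate in a series of 4 laboratory sessions, each visit separated by at least a week". Order is described twice:

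- Section IV assigns the tobaccos "in a randomly assigned sequence, using the block randomization method".
- Section VII.2 (Sample Size Justification) recruits 60 people partly to "ensure the Latin square ordering is balanced across the four tobacco types".

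The two are compatible if Latin square sequences are what is block-randomized, but section IV does not say so. Section III.B3 plans the 60 "with the goal of having complete data sets for 50 participants"; section VII.2 allows for 20% attrition, which leaves 48.

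**The concern.** A Latin square makes visit orthogonal to tobacco. With complete data, a trend shared by all participants therefore does not bias a tobacco contrast. The trend does not disappear, however. If visit is not in the model, the trend is counted as residual error, and the six pairwise tests are judged against an error term that is larger than the true one.

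Repeated smoking on an investigational device, repeated sensory ratings and repeated spirometry could each plausibly drift over four visits, and Aim 3 has many outcomes. What is at stake is power that the design has already paid for.

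**Working it through.** **Inputs.** From section VII.2: d = 0.5 SD; r = 0.6, 0.7 or 0.8, so residual variance 1 − r = 0.4, 0.3 or 0.2; two-sided alpha 0.0083 (normal critical value 2.64); within-pair correlation rho; N = 43 in the text and 50 in the caption of Table VII.5. N = 48 is 60 less 20%. The visit trend is my assumption: a linear shift of b SD per visit, b = 0.1, 0.2 or 0.3, that is 0.3, 0.6 or 0.9 SD from visit 1 to visit 4. I take rho = 0 for people smoking alone.

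**The plan's own figure.** The variance of a pairwise contrast is 2(1 − r)(1 + rho)/N. With N = 50 and a noncentral t on 24 df (25 pairs − 1), r = 0.6, rho = 0.1 and d = 0.5 give 0.803, as printed; all 27 cells reproduce within 0.0005. A normal approximation at N = 43 also fits (0.804 for this cell). The text and caption should be reconciled, but that is a separate matter.

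**Effect of omitting visit, balanced order.** A linear trend has visit effects −1.5b, −0.5b, 0.5b and 1.5b, with sum of squares 5b². Over N participants this puts 5Nb² into a residual with 3(N − 1) df, so the residual mean square rises by 5Nb²/(3N − 3). The true sampling variance of the contrast is unchanged. Hence:

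- SE_true = √[2(1 − r)(1 + rho)/N]
- SE_est = √[2(1 − r + 5Nb²/(3N − 3))(1 + rho)/N]
- power = Φ[(d − 2.64·SE_est)/SE_true]

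Example, N = 50, rho = 0, r = 0.6, b = 0.3: SE_true = √(0.8/50) = 0.1265. The added variance is 5·50·0.09/147 = 0.153. SE_est = √(2·0.553/50) = 0.1487, which is 18% too large. Power = Φ[(0.5 − 2.64·0.1487)/0.1265] = 0.80.

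| Case (r = 0.6) | b = 0 | 0.1 | 0.2 | 0.3 |
|---|---|---|---|---|
| SE too large by | 0% | 2% | 8% | 18% |
| Power, N = 50, rho = 0 | 0.91 | 0.90 | 0.86 | 0.80 |
| Power, N = 48, rho = 0 | 0.89 | 0.88 | 0.85 | 0.78 |
| Power, N = 43, rho = 0.1 | 0.80 | 0.79 | 0.74 | 0.65 |

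In the last row, 0.65 becomes 0.67 if the pair inflation is not applied to the trend variance.

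**Drift at which power falls to 80%.** At N = 50 and rho = 0: 0.30 SD per visit for r = 0.6, 0.42 for r = 0.7 and 0.51 for r = 0.8. At N = 48, rho = 0, r = 0.6: 0.27. At N = 43, rho = 0.1: 0.05, 0.29 and 0.41 for the three values of r.

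**Cross-check with t critical values.** At N = 50, rho = 0, r = 0.6, power without visit is 0.897 with no drift, 0.867 at a total drift of 0.5 SD and 0.758 at 1.0 SD. With visit it is 0.897 throughout.

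**Simulation, Latin square.** 60 assigned 15 per sequence, 48 kept at random, r = 0.6, rho = 0, Tukey, 10,000 runs:

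| b | Power without visit | Power with visit | Family-wise error without visit |
|---|---|---|---|
| 0 | 0.897 | 0.895 | 5.1% |
| 0.1 | 0.886 | 0.896 | 4.0% |
| 0.2 | 0.852 | 0.895 | 3.1% |
| 0.3 | 0.781 | 0.893 | 1.9% |

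With visit, the family-wise error stays at 4.6–5.1%. Mean bias is at most 0.002 SD.

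**If order is random without balance** (N = 48, 4,000 runs), the tests without visit keep their level (4.6–5.5%). Power without/with visit is 0.898/0.887, 0.876/0.885, 0.838/0.888 and 0.756/0.888 at b = 0 to 0.3.

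**The case against.** Five points can be made against this.

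- **Visit may be intended.** Section VII.1 lists no fixed effects explicitly, so silence is not exclusion. That is fair, but the remedy is the same: write the term down before data are seen.
- **The harm needs a trend that the documents do not quantify.** This stands. At N = 50, rho = 0 and r = 0.6 it takes 0.30 SD per visit, 0.9 SD over the study, to reach 80% power. That exceeds the 0.8 SD that the plan itself calls large. Same time of day, abstinence before visits and a rating practice session should limit drift.
- **The assumed r may already contain visit variation.** It comes from an earlier variability study. If a 0.2 SD trend is already inside r = 0.6, the pure residual is 0.4 − 5(0.04)/3 = 0.333 and nothing is lost against the printed power. The term would still add: at N = 50, rho = 0, Φ[(0.5 − 2.64·0.1265)/0.1155] = 0.925 without visit, against Φ[0.5/0.1155 − 2.64] = 0.955 with it.
- **The N = 43 case is fragile.** It sits on the 80% line whatever is done about visit, so its 0.05 threshold should carry little weight.
- **Partial data help.** With 60 recruited, 20% dropout and all sessions used, power at a total drift of 0.5 SD is 0.880 without and 0.904 with visit. The gain is smaller there, and both values exceed 80%.

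The gain is also limited to a trend common to participants. With purely individual slopes (SD 0.2, mean 0), power is 0.845 without and 0.843 with visit.

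These points limit the size of the gain. None is a reason to leave the term out.

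**Conclusion.** The concern holds as a conditional loss of efficiency. The design balances tobacco over visits, and the analysis as written does not use that balance. With a shared drift of 0.1 SD per visit the cost is about 1 point of power. At 0.2 it is about 4 to 5 points and at 0.3 about 10 to 11 points (r = 0.6, d = 0.5, rho = 0, 48 to 50 completers, balanced order).

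Complete-data contrasts are unbiased and false positives do not increase: the tests are conservative under balanced order and keep their level under unrestricted order. No printed power figure needs to change. The sizes rest on assumed linear trends, since the documents give none.

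**What to change.** State in section VII.1 that the Aim 3 mixed models comparing the four tobaccos include visit (1–4, categorical) as a fixed effect, besides tobacco and the random subject effect, with the Tukey comparisons unchanged. The models relating sensory ratings to liking within a given preparation are outside this change. It would help to say in section IV that the block-randomized sequences are those of the Latin square.

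The cost is one sentence; visit number follows from the session schedule. The term uses 3 residual df (of 126 at N = 43, or 141 at N = 48); at N = 43 the Tukey critical value moves from 3.682 to 3.683. With no trend, simulated power under Latin square order is 0.897 without and 0.895 with visit. If order were unrestricted and there were no trend, the cost would be about 1 point (0.898 against 0.887). The term does not address carry-over.
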